### APPROACH:

**Methodology:** We implemented a placebo controlled, two group study design that characterized how changes in corticospinal excitability are associated with motor adaptation and walking energetics in 26 persons following repetitive exposure to AIH. Each intervention involved 5 consecutive treatment visits. For each treatment visit, participants received an exposure [15, 1.5 min episodes at 9% O2 (AIH) or 21% O2 (SHAM) at 1 min intervals]. Split belt adaptation assessments and metabolic cost quantification protocols were implemented at the end of each intervention. Delivery of intermittent gas mixtures was accomplished using air generators [HYP123, HypoxicO] attached to a non-rebreathing face mask. In order to ensure subject safety during interventions, we monitored oxygen saturation (SpO2), heart rate, respiratory rate and blood pressure [Root 7, Masimo] at 1 second intervals.

**Transcranial Magnetic Stimulation:** TMS was delivered via a custom-built batwing coil for leg stimulation connected to a DUOMAG unit [Deyemed]. Single pulse TMS with monophasic current waveform was applied to the contralateral motor cortex of the more impaired target TA muscle. Coil position and head position were digitally tracked to ensure similar coil placement in repeated measurements using a Visor 2LT optical system [ANT Neuro]. The hot spot was defined as the region where largest and most consistent MEPs are evoked using a stimulation intensity of 1.2 x resting motor threshold (RMT) intensity. RMT was defined as the stimulator output intensity that elicits MEPs with peak-to-peak amplitudes greater than 50  $\mu$ V in four out of eight trials in the relaxed muscle. MEPs from the tibialis anterior were obtained during rest and at static contraction of up to 20% MVC. Real-time visual feedback about EMG contraction level was provided. The slope of the recruitment curve reflects gain in MEP amplitude with increasing stimulus intensity, providing an indication of gain modulation. TMS intensity was increased from below motor threshold at stimulator intensity intervals representing 90% to 120% of RMT. 20 randomized stimuli were given per stimulation intensity, and the MEPs were ensemble averaged for analyses. The mean MEP response was plotted against the corresponding stimulation intensity (% of RMT) to produce a stimulus-response recruitment curve. We compared recruitment curve parameters (MEPmax, slope) before and after AIH.

**Sensorimotor Adaptation:** We characterized motor adaptation by quantifying changes in step asymmetry in response to split belt treadmill speed perturbations, before and after repetitive AIH exposure. Step asymmetry was quantified as the ratio of normalized difference in step lengths of each leg. Temporal asymmetry was computed from the time series of joint angles as the lag time at peak cross-correlation of limb angle trajectories. The first 5-10 strides of the 'adaptation' and 'de-adaptation' epochs were used to quantify speed perturbation induced effects. Motor adaptation was evaluated relative to the baseline epoch by comparing step asymmetries during the first and last 10 steps of the 'adaptation' and 'de-adaptation epochs'. A greater difference indicates greater motor adaptation. Improvement of interlimb coordination was estimated based on decreases of asymmetry in both spatial and temporal step parameters. We compared changes in step asymmetry and interlimb coordination between AIH and SHAM interventions.

**Net Metabolic Power:** We quantified the metabolic costs during treadmill gait before and after AIH during the final 2 minutes of the motor adaptation epochs. We identified spatiotemporal gait parameters that affect the capacity to minimize the metabolic cost in participants with iSCI. We measured the net metabolic power during treadmill walking as the rate of metabolic energy consumption. Participants wore a nose clip and breathed in and out of a mouthpiece to measure the rates of O2 consumption VO2 and CO2 production VC02 (liter/min) using expired gas analysis [ParvoMedics, TrueMax2400]. The measured rates (liter/min) of VO2 and VC02, which we then converted to metabolic power (J/s) using the Brockway equation as the outcome measure representing the rate of metabolic energy consumption. Metabolic power was normalized to the subject's body weight (J · s · kg). To calculate net metabolic power, we subtracted baseline resting metabolic power while quiet standing.

### **STATISTICAL ANALYSES:**

#### **Hypothesis Testing for Corticospinal Excitability:**

We hypothesized that exposure to repetitive, acute intermittent hypoxia enhances CST excitability to the TA (i.e., increase  $MEP_{max}$  and recruitment curve slope) after repetitive AIH. TMS testing was completed within this time, as we expected this facilitation to persist for up to 1 hour post-AIH based on prior research in our lab. Data was evaluated for normality using the Kolmogorov-Smirnov test. If data satisfied the normality test, a repeated measures analyses of variance was used to determine if each excitability parameter differed across PRE and POST conditions. Sphericity was assessed using the Mauchly test. If sphericity was violated, we used the Huynh-Feldt corrected p value. Post hoc comparisons were used in the Tukey-Kramer correction for multiple comparisons.

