#### **Hypothesis Testing for Motor Adaptation:**

Spatiotemporal asymmetry parameters were calculated in each epoch (adaptation, second adaptation) in 3 periods: initial (mean of first 5 strides), early (mean of strides 6-20), and the late (mean of last 30 strides). Differences from BL to adaptation was compared between and within interventions using a mixed model ANOVA at a 0.05 significance level; the between-subjects factor is intervention (AIH vs. SHAM), and the within-subjects factor is time (initial, early change, late), with spatiotemporal parameters (e.g., step length asymmetry, step time asymmetry) as the dependent variables. Analysis of covariance (ANCOVA) was used if PRE measures are significantly different between interventions. If sphericity was violated, we used the Huynh-Feldt corrected p value. Post hoc comparisons used the Tukey-Kramer correction for multiple comparisons.

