#### **Hypothesis Testing for Metabolic Cost:**

We tested the hypothesis that exposure to repetitive, acute intermittent hypoxia decreased net metabolic power using a mixed model ANOVA at a 0.05 significance level; the between subject's factors is intervention (AIH vs SHAM), and the within subjects' factors is time (initial, early change, plateau), with net metabolic power as dependent variable. A multiple linear regression was implemented to determine the spatiotemporal variables associated with capacity to reduce asymmetry and net metabolic power for the following independent variables:  $MEP_{max}$ , recruitment curve slope, step length, step time, stance duration and baseline metabolic power. Variance inflations factors were calculated to avoid multicollinearity with the Akaike information criterion model utilized for model selection.

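### The only stated test of MEPmax and recruitment-curve slope is PRE versus POST, with no AIH-versus-SHAM comparison, so a change shared by both arms would count as an AIH effect

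*Combined protocol and SAP*

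**What the plan says.** The Methodology paragraph under APPROACH sets out the design: "We implemented a placebo controlled, two group study design". The comparator is a SHAM exposure at 21% O2.

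For corticospinal excitability, the hypothesis is that AIH raises MEPmax and recruitment-curve slope. Under Hypothesis Testing for Corticospinal Excitability, the stated test, if the data pass a normality check, is that "a repeated measures analyses of variance was used to determine if each excitability parameter differed across PRE and POST conditions". Mauchly's test, a Huynh-Feldt correction and Tukey-Kramer post hoc comparisons follow. The Transcranial Magnetic Stimulation paragraph describes the comparison in the same way: "We compared recruitment curve parameters (MEP max , slope) before and after AIH". It also states that "MEPs from the tibialis anterior were obtained during rest and at static contraction of up to 20% MVC", but the statistical section does not say which of the two states is tested.

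The other two hypotheses are treated differently. The Sensorimotor Adaptation paragraph ends with "We compared changes in step asymmetry and interlimb coordination between AIH and SHAM interventions". In the motor-adaptation analysis "the between-subjects factor is intervention (AIH vs. SHAM)", and in the metabolic analysis "the between subject's factors is intervention (AIH vs SHAM)".

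**The concern.** A PRE-POST test asks whether excitability changed. The hypothesis is that AIH changed it, and in a sham-controlled study that needs a contrast with SHAM. Repeat testing or the passage of time can move MEPmax or slope in both arms. A test without an arm term cannot separate such a shift from an effect of AIH, whether it is run in the AIH arm alone or in all participants together. The text does not say which was done.

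Excitability is one of three hypotheses with its own test, and the only one whose stated test leaves out the control. A significant PRE-POST result could therefore be reported as an AIH effect although AIH was never compared with SHAM.

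**Working it through.** **1. The three stated tests side by side**

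| Hypothesis | Stated model | AIH vs SHAM factor |
|---|---|---|
| Corticospinal excitability | Repeated measures ANOVA, PRE vs POST | None named |
| Motor adaptation | Mixed model ANOVA | Yes |
| Metabolic cost | Mixed model ANOVA | Yes |

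MEPmax and slope appear once more, as independent variables in the multiple regression under Hypothesis Testing for Metabolic Cost. That is not a between-arm test of either parameter.

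**2. Inputs for an illustration**

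The document gives no power calculation, SD or retest data, so it has no figure of its own to reproduce.

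- Total sample: "in 26 persons following repetitive exposure to AIH". The split is not stated; 13 per arm is assumed, with 10 to 16 in the AIH arm as a range.
- Level: two-sided 0.05 is assumed. The excitability section states none; the other two analyses use 0.05.
- Effects are in SDs of the POST-minus-PRE change.

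**3. A shared shift d and no AIH effect**

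With two time points, the repeated measures ANOVA is a paired t test with noncentrality d × √n on n − 1 degrees of freedom. For n = 13 and d = 0.3 the noncentrality is 0.3 × √13 = 1.08. Rejection probabilities:

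| Shared shift (SD) | AIH arm only, n = 13 | Both arms pooled, n = 26 | Between arms, 13 vs 13 |
|---|---|---|---|
| 0.1 | 6.3% | 7.8% | about 5% |
| 0.3 | 16.9% | 31.3% | about 5% |
| 0.5 | 38.2% | 68.8% | about 5% |

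With 10 to 16 in the AIH arm, the AIH-only figure is 13.6% to 20.3% at 0.3 SD and 29.3% to 46.5% at 0.5 SD. The between-arm column is a two-sample t test on the change, by simulation. For two arms and two times it is equivalent to the intervention-by-time test.

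**4. What the between-arm test costs in power**

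The noncentrality is d / √(1/n₁ + 1/n₂). For a change of 1.0 SD in the AIH arm only:

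- Between arms, 13 vs 13: 1.0 / √(2/13) = 2.55, power 69% (66% for 10 vs 16).
- AIH-only PRE-POST, n = 13: power 91% (80% to 96% for n = 10 to 16).
- Pooled PRE-POST: power 60% at 13/13 (38% to 79% for AIH/SHAM splits of 10/16 to 16/10).

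The effect needed for 80% power is 1.15 SD between arms and 0.85 SD for the AIH-only test. The 95% CI half-width for AIH minus SHAM is about t(0.975, 24) × √(2/13) = 2.064 × 0.392 = 0.81 SD.

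**5. The sphericity step**

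Mauchly's test has k(k − 1)/2 − 1 degrees of freedom for k levels. For PRE and POST, k = 2 gives 2 × 1/2 − 1 = 0, so there is nothing to test. Tukey-Kramer is likewise idle, since two levels allow only one pairwise comparison.

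**The case against.** The strongest reply is that the model was under-described, not that SHAM was ignored. Sphericity and multiple-comparison steps make no sense for a two-level factor, so a larger model may have been run. The before-and-after wording is also weak evidence by itself: the Net Metabolic Power paragraph uses it too, and that outcome is later compared between arms. Parts of the document were not available for review. All of this stands as a limit on the claim, which concerns the available text and does not show that no controlled test was done. It does not supply the missing comparison, because the section devoted to this hypothesis names a test and that test has no arm term.

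It is also fair to say that the shift sizes, arm sizes and level are assumed. The percentages show scale only.

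On the remedy, the within-subject factor in the other two analyses is period within the session, not PRE/POST, so only the between-arm factor carries over from them. The change-score test is also not the most efficient choice. At 1.0 SD and 13 per arm, a baseline-adjusted ANCOVA has about 71% to 80% power for PRE-POST correlations of 0.9 to 0.5, against 69%. This makes the cost of a controlled comparison smaller than section 4 of the working suggests.

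Finally, no primary endpoint is named in the available text, so the damage is confined to the excitability conclusion.

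**Conclusion.** The concern holds and must be fixed. As written, the excitability hypothesis of a sham-controlled study is tested without the sham arm, and following the stated rule credits AIH with any change common to both arms. This conclusion comes from the text alone. Its size depends on an unknown shared shift: for 0.1 to 0.5 SD, with 13 per arm and two-sided 0.05 assumed, the chance of a false AIH claim is 6% to 38% in the AIH arm alone and 8% to 69% pooled, against the nominal 5%. Which MEP state is tested, and the idle sphericity step, are lesser reporting points.

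**What to change.** - **Model.** For MEPmax and slope, test the intervention-by-time term of a 2 × 2 mixed ANOVA (AIH or SHAM by PRE or POST). A baseline-adjusted between-arm comparison is an acceptable alternative. State the significance level.
- **If normality fails.** Compare the POST-minus-PRE change between arms with a rank-sum test and give the Hodges-Lehmann estimate.
- **Reporting.** Base the conclusion on the AIH-minus-SHAM estimate with its 95% CI, and give within-arm changes descriptively.
- **MEP state.** Say whether rest, contraction or both are analysed; if both, analyse them separately.
- **Sphericity.** Drop the Mauchly and Huynh-Feldt step for the two-level factor, or name the further factors it was meant for.
- **Status.** The document is written in the past tense. Label the model as a clarification if it was the one intended, and as post hoc otherwise.
- **If SHAM participants had no TMS.** Report a within-group change and claim no effect over SHAM.

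If PRE and POST TMS values exist for SHAM, which the available text does not state, the cost is revised SAP wording and one re-run model per parameter and state: two models, or four if rest and contraction are both analysed. The downside is lower power than the AIH-only test, 69% against 91% at 1.0 SD with 13 per arm, though the AIH-only test does not answer the controlled question. If SHAM values do not exist, only the wording changes.

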#### **Hypothesis Testing for Motor Adaptation:**

Spatiotemporal asymmetry parameters were calculated in each epoch (adaptation, second adaptation) in 3 periods: initial (mean of first 5 strides), early (mean of strides 6-20), and the late (mean of last 30 strides). Differences from BL to adaptation was compared between and within interventions using a mixed model ANOVA at a 0.05 significance level; the between-subjects factor is intervention (AIH vs. SHAM), and the within-subjects factor is time (initial, early change, late), with spatiotemporal parameters (e.g., step length asymmetry, step time asymmetry) as the dependent variables. Analysis of covariance (ANCOVA) was used if PRE measures are significantly different between interventions. If sphericity was violated, we used the Huynh-Feldt corrected p value. Post hoc comparisons used the Tukey-Kramer correction for multiple comparisons.

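### The planned repeated-measures ANOVAs normally use only participants with every cell filled, and the available text has no rule for partly missing data; a REML mixed model would keep those data

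*Combined protocol and SAP*

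**What the plan says.** The three outcome analyses stand under Statistical Analyses in the combined protocol and SAP.

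- **Corticospinal excitability:** "a repeated measures analyses of variance was used to determine if each excitability parameter differed across PRE and POST conditions". Sphericity is checked with the Mauchly test and, if it fails, the Huynh-Feldt p value is used. No AIH versus SHAM factor is named.
- **Motor adaptation:** "Differences from BL to adaptation was compared between and within interventions using a mixed model ANOVA at a 0.05 significance level". Intervention is the between-subjects factor and time, with three levels, the within-subjects factor. Then: "If sphericity was violated, we used the Huynh-Feldt corrected p value".
- **Metabolic cost:** the hypothesis is that repetitive AIH "decreased net metabolic power using a mixed model ANOVA at a 0.05 significance level", again with intervention between subjects and three time levels within. Sphericity is not mentioned.

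The Approach section gives the setting: "We implemented a placebo controlled, two group study design", with "walking energetics in 26 persons following repetitive exposure to AIH". On timing it says "Each intervention involved 5 consecutive treatment visits" and "Split belt adaptation assessments and metabolic cost quantification protocols were implemented at the end of each intervention".

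The available text names no random effect, covariance structure, likelihood or REML fit, imputation, analysis set, dropout rate or rule for incomplete participants. It does not say that anyone was excluded, or that any data were missing.

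**The concern.** The term mixed model ANOVA could mean either of two methods. The Mauchly test and the Huynh-Feldt correction belong to univariate repeated-measures ANOVA; a likelihood-based mixed model would specify a covariance structure instead. The natural reading is therefore a repeated-measures ANOVA for excitability, a split-plot ANOVA for motor adaptation and, from its layout, probably a split-plot ANOVA for metabolic power.

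In its usual implementation that method takes one complete row per participant. Someone with PRE but not POST TMS, or with two of three time levels of metabolic power, leaves the analysis together with the valid measurements. Two things are at stake:

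- **Precision.** This matters with 26 people.
- **Bias.** If the chance of a missing cell depends on values that were observed, those with complete data are a selected group. In the motor-adaptation and metabolic models this can distort AIH versus SHAM. In the excitability model, which has no intervention factor, it can distort only the PRE to POST change.

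**Working it through.** The documents give no power, SD, effect size, within-person correlation or attrition, so there is no figure to reproduce. Only the 26 participants, the two groups, the number of time levels and the 0.05 level come from the plan. Everything else here is assumed.

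**Assumptions.** 13 per arm; three time levels with unit SD and common correlation ρ of 0.5 or 0.8; no true effect; the last level missing in a proportion p of 10% or 20%. The outcome is the AIH minus SHAM difference averaged over the three levels.

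**Step 1: precision, missing at random across everyone.** With full data, SE = √[(2/13)(1+2ρ)/3], which is 0.320 at ρ = 0.5 and 0.365 at ρ = 0.8. Complete-case analysis keeps 26 × 0.9 = 23.4 or 26 × 0.8 = 20.8 participants on average, so its SE should grow by roughly √(1/0.9) = 1.05 or √(1/0.8) = 1.12. Simulation (4,000 runs per setting) compared this with generalised least squares on all observed data:

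| p | ρ | SE, complete cases | SE, all data | Ratio |
|---|---|---|---|---|
| 10% | 0.5 | 0.333 | 0.318 | 1.05 |
| 10% | 0.8 | 0.395 | 0.371 | 1.06 |
| 20% | 0.5 | 0.363 | 0.325 | 1.12 |
| 20% | 0.8 | 0.418 | 0.371 | 1.13 |

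The all-data column treats the covariance as known, which is a best case. A separate simulation (20,000 replicates, 20% missing) that used a factored-likelihood estimate gave 0.365 against 0.328 at ρ = 0.5 (ratio 1.11), 0.399 against 0.353 at 0.7 (1.13) and 0.412 against 0.367 at 0.8 (1.12). Bias was about 0 for both methods.

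For scale, suppose the all-data analysis had 80% power (two-sided 0.05, normal approximation). An SE 12% larger gives 2.802/1.12 − 1.960 = 0.542, or about 71% power.

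**Step 2: bias in AIH versus SHAM (motor adaptation and metabolic cost only).** Suppose that in one arm participants above average at the initial level miss the last level with probability 2p and the rest never do, while in the other arm a proportion p is missing at random. In the first arm the mean initial value among completers is 0.798 × ½[(1−2p) − 1]/(1−p) = −0.798 p/(1−p). Averaged over levels, the difference between arms shifts by (1+2ρ)/3 × 0.798 p/(1−p):

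- p = 10%: 0.059 SD (ρ = 0.5) and 0.077 SD (ρ = 0.8); simulated 0.053 and 0.077.
- p = 20%: 0.133 SD and 0.173 SD; simulated 0.128 and 0.164.

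All-data bias was within 0.01 SD of zero. If selection runs in opposite directions in the two arms, the simulated complete-case bias is 0.13 to 0.34 SD. With 40% missing in above-average AIH participants and 5% in all others, it is 0.14 to 0.17 SD.

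**Step 3: PRE/POST excitability.** With no true change, the expected change given PRE is −(1−ρ) × PRE. If those above average at PRE miss POST with probability 2p, complete pairs show a spurious change of (1−ρ) × 0.798 p/(1−p): 0.044 and 0.018 SD at p = 10% (ρ = 0.5, 0.8), and 0.100 and 0.040 SD at p = 20%. A separate simulation of PRE/POST pairs gave 0.03 to 0.09 SD for complete pairs and no bias for the likelihood estimate that keeps PRE-only participants.

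**The case against.** The strongest reply is that the harm is conditional throughout. Several stronger readings are tempting, and the documents do not support them.

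- **That incomplete participants were dropped.** Deletion is inferred from the model class; no rule is stated. The evidence is also uneven. With two levels, PRE and POST, the Mauchly test has nothing to test, and the metabolic section mentions no sphericity step. This stands as a limit on certainty. Parts of the document were not available for review, so a missing-data rule there cannot be excluded.
- **That anyone who stops walking early leaves the comparison.** The late level is the last 30 strides, wherever the epoch ends. Initial and early need strides 1 to 20, so 20 + 30 = 50 strides fill all three cells without overlap. Stopping early changes what late means more often than it empties the cell.
- **That a mixed model rescues those who never reached the POST session.** In a model with POST outcomes only, such a person contributes nothing under either method. The figures for losing one of three levels do not carry over to that case.
- **That the arms differ in tolerability, so losses must be unequal.** The Approach section gives different oxygen concentrations and describes monitoring, but no tolerability or withdrawal data.
- **That AIH versus SHAM is biased for TMS.** That model has no intervention factor.

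It is also fair that the all-data bias is zero because missingness was made to depend only on observed values. The one-arm bias at 20% missing is about 0.4 of a standard error (0.164/0.408).

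What remains is that partly observed participants can occur, the usual fit of the named method discards their valid data, and nothing in the available text says otherwise.

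**Conclusion.** The point holds in a limited, conditional form. The plan names classical ANOVA for excitability and motor adaptation, and probably for metabolic cost, with no stated treatment of partly missing data. If the usual complete-case fit was used and some participants had some cells but not all, the standard error is inflated by about 5 to 6% at 10% missing and 11 to 13% at 20%. If missingness also depends on observed values in one arm only, AIH versus SHAM shifts by about 0.05 to 0.17 SD in the motor-adaptation and metabolic models. The excitability change can shift by a few hundredths of an SD, up to about 0.1.

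These sizes rest on assumed rates, correlations and equal allocation. With complete data there is no loss, and the documents do not show that any data were missing. The case for change is that the alternative costs almost nothing and does at least as well in either situation.

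**What to change.** In all three Hypothesis Testing sections, replace the ANOVA and its sphericity steps with a linear mixed model fitted by REML, keeping the same fixed effects. State the covariance structure (unstructured or compound symmetry) and use Kenward-Roger degrees of freedom. Fit it to every observed value, with participants in their assigned arm. In the PRE/POST excitability model, keep participants who have PRE only. Report completeness by arm and time level for each outcome, so that a reader can see whether the question arises at all.

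One related passage needs reconciling first. The Net Metabolic Power section takes the measurement from the final 2 minutes of the adaptation epochs, while the Metabolic Cost analysis has three time levels. The plan should say which of those cells can hold data for anyone.

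The cost is revised wording and a refit of existing data. The downside is reliance on missing at random, which cannot be verified but is weaker than the missing-completely-at-random assumption that complete-case analysis generally needs. If nothing is missing, the results are essentially unchanged. The model does not recover POST outcomes for participants with no POST session; the completeness report should show how many there were.

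### Adjusting the motor-adaptation models for PRE only after a significant PRE test can cost power for the intervention effect and gains nothing in type I error control

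*Combined protocol and SAP*

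**What the plan says.** Statistical Analyses, Hypothesis Testing for Motor Adaptation, gives the model: "Differences from BL to adaptation was compared between and within interventions using a mixed model ANOVA at a 0.05 significance level". Arm is the between-subjects factor. Time is the within-subjects factor, with three periods that average 5, 15 and 30 strides. Parameters are calculated in two epochs, and the dependent variables are listed only by way of example. The adjustment rule is one sentence: "Analysis of covariance (ANCOVA) was used if PRE measures are significantly different between interventions". The text available does not give the level of the PRE test. It does not say which parameter, epoch or period is tested, or whether one positive test switches every model.

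Two statements bear on the default outcome. Approach, Sensorimotor Adaptation, says "Motor adaptation was evaluated relative to the baseline epoch by comparing step asymmetries during the first and last 10 steps", so BL is the treadmill baseline within a session and subtracting it is not an adjustment for PRE. The same paragraph ends "We compared changes in step asymmetry and interlimb coordination between AIH and SHAM interventions", which can be read as a PRE-to-POST change.

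The paragraph also describes testing on both sides of the exposure, but Approach, Methodology, says "Split belt adaptation assessments and metabolic cost quantification protocols were implemented at the end of each intervention".

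The trial is described as a "placebo controlled, two group study design" "in 26 persons following repetitive exposure to AIH". The available text gives no allocation ratio, effect size, PRE-POST correlation or power calculation.

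**The concern.** What ANCOVA gains depends on how strongly PRE predicts POST. It does not depend on whether the arms happen to differ significantly at PRE. A rule keyed to significance will usually leave a prognostic baseline unused in a trial of 26, where precision is scarce. Because the rule does not say which PRE measures are tested or what a positive test switches, two analysts could also reach different models from the same data. What is at stake is the power of the between-arm comparison of motor adaptation and the reproducibility of the model choice.

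**Working it through.** **Inputs.** From the documents: N = 26, two arms, alpha 0.05, and the conditional rule. Assumed, because not given: 13 per arm, random allocation, two-sided tests, a PRE test at 0.05, normal data, true effects of 0.5, 0.8 and 1.15 SD, and rho varied from 0 upward. The plan states no power figure to reproduce.

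**Step 1. When one PRE test fires.** The smallest significant difference is t(0.975, 24) x sqrt(2/13) = 2.064 x 0.392 = 0.81 SD (0.83 SD with a 16:10 split). With no true PRE difference this happens in 5% of trials, so 95% stay unadjusted whatever rho is.

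**Step 2. Several PRE tests.** Two parameters x two epochs x three periods make 12 tests. If they are independent and any one triggers, the rate is 1 - 0.95^12 = 46%. Three parameters give 1 - 0.95^18 = 60%. The parameter list is open, so neither figure is a ceiling for the plan.

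**Step 3. Break-even, main effect.** Relative to an unadjusted POST comparison, the expected variance under ANCOVA is (1 - rho^2) x (N - 3)/(N - 4) = (1 - rho^2) x 23/22.
- Against POST only, this equals 1 at rho = sqrt(1/23) = 0.21.
- Against a change score, whose relative variance is 2(1 - rho), equality needs 1 + rho = 44/23, so rho = 0.91. There is no break-even in the low range.

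**Step 4. Power of the whole rule.** The main effect is tested on participant means, so it was simulated as a two-group comparison (100,000 trials per setting, one PRE test, true effect 0.8 SD). Power is in percent and gain in points.

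| rho | Always ANCOVA | Rule, POST-only default | Gain from always adjusting | Rule, change-score default | Gain from always adjusting |
|---|---|---|---|---|---|
| 0 | 48.1 | 49.4 | -1.3 | 27.9 | 20.2 |
| 0.1 | 48.6 | 49.4 | -0.8 | 30.9 | 17.7 |
| 0.2 | 49.8 | 49.7 | 0.1 | 33.8 | 16.0 |
| 0.3 | 52.0 | 49.9 | 2.1 | 37.8 | 14.2 |
| 0.5 | 59.9 | 49.9 | 10.0 | 50.0 | 9.9 |
| 0.7 | 76.3 | 50.6 | 25.7 | 71.6 | 4.7 |

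With the POST-only default, the gains at rho 0.3/0.5/0.7 are 1/6/17 points for a true effect of 0.5 SD and 2/8/15 for 1.15 SD. If any of 12 tests triggers ANCOVA (0.8 SD), they fall to 1/6/15 (POST-only) and 8/6/3 (change score).

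**Step 5. Type I error.** For rho up to 0.8, the rule gives 3.1-5.0% with a POST-only default and 3.7-4.9% with a change score. Always-ANCOVA gives 4.9-5.1%.

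**Step 6. Intervention x time.** A covariate that is constant over time shifts every period of a participant equally, so it leaves contrasts between periods unchanged. An imbalance that differs between periods does reach this test. Take a PRE imbalance above 0.81 SD in the initial-to-late contrast, with participant variance 0.6. The table shows how often it goes unflagged.

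| Assumed period variances | Test of PRE mean | Test of each period |
|---|---|---|
| 0.4 / 0.4 / 0.4 | about 95% | about 67% |
| 0.8 / 0.4 / 0.2 | about 92% | about 61% |
| 2.0 / 0.5 / 0.2 | about 85% | about 46% |

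With equal variances the PRE mean and the contrast are uncorrelated, so 95% follows at once. Periods averaging 5, 15 and 30 strides make equal variances doubtful, hence the range.

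**The case against.** **The correlation is unknown.** This stands. The outcome is already referenced to the in-session BL epoch, which may lower rho. With a POST-only default and rho 0.3, the loss is only 1 to 2 points. A reader might infer from the last row of the power table that the plan gives away some 26 points; that needs rho of 0.7, and nothing in the documents supports such a value. What remains is the lopsided trade: about 1 point lost if PRE is uninformative, against gains that grow with rho.

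**The 0.2 break-even is not general.** This also stands. It belongs to the POST-only reading, and the documents leave the default outcome ambiguous. Under the change-score reading, always adjusting is better at low rho as well, so the criticism of the rule survives either way.

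**False positives are not inflated.** Agreed. In the roughly 15% of null trials with an unflagged PRE imbalance above 0.5 SD (one test), simulated false-positive rates at rho 0.3 to 0.8 are 6-12% (POST-only) or 7-10% (change score). A reader might take these as the plan's error rate. They hold only within trials selected for imbalance; over all trials the rule is at or below 5%.

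**The main effect may not be the target.** The plan names neither the main effect nor the interaction as key, and the initial-to-late contrast is not a prespecified test. So the power table should not be read as a loss for the interaction.

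**Conclusion.** The concern holds as a conditional loss of efficiency and an under-specified rule. It is not a validity failure. Under 13:13 random allocation, one PRE test and a true effect of 0.8 SD, always adjusting changes main-effect power by about -1 to +26 points over rho 0 to 0.7 (POST-only default), or by about +20 down to +5 points (change-score default). The two-stage rule buys no type I protection, because unconditional ANCOVA already holds 5%; its slightly lower rate is conservatism. More PRE tests shrink the loss but make the choice of model depend more on chance and on the analyst. The intervention x time test is touched only by imbalance that differs between periods, which a PRE level test often misses. If allocation was not random, a real PRE difference could exist, and omitting PRE after a non-significant test could then also bias the comparison; the available text does not settle this. The change should be made, but the trial's conclusions cannot be called unsound on this ground.

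**What to change.** Delete the conditional sentence and the PRE test. For every asymmetry parameter, analyse the POST difference from the BL epoch and always include the PRE value of the same parameter, matched by period so that it also serves the intervention x time test. State this outcome definition in both the Sensorimotor Adaptation and the Motor Adaptation analysis text.

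First confirm that PRE assessments exist for every participant, because the Methodology and Sensorimotor Adaptation paragraphs differ on when assessments took place.

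The cost is revised wording, a re-run, one or two degrees of freedom per model, and about 1 point of power if PRE turns out to be uninformative. No new data are needed if PRE values are complete. The document is written in the past tense. If results are already known, keep the planned analysis and report the always-adjusted one beside it, labelled post hoc.
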